I, the undersigned, am responsible for the conduct of the study at the site below and by my signature below, I confirm that I have read, understand and will strictly adhere to the study protocol, Clinical Evaluation of an Evidence Based Adult Delivery Model in a Newly Implanted Nucleus CI Population.

Clinical Investigational Site

Principal Investigator's Name (print)

Title

Signature

Sponsor Representative

Title

Signature

Version 6.2

CAM-CLE-CAM5753-CIP-01

CAM-
CLE-
CAM5753-
CIP-01

Version 6.2

CAM-CLE-CAM5753-CIP-01

CAM-
CLE-
CAM5753-
CIP-01

Table of Contents

TABLE OF CONTENTS.....	4
1. CLINICAL INVESTIGATIONAL SYNOPSIS.....	6
2. GLOSSARY	9
3. INTRODUCTION.....	11
4. STUDY DESIGN OVERVIEW	13
4.1 DEVICE DESCRIPTION	14
4.2 PROGRAMMING SOFTWARE DESCRIPTION	14
4.3 SUBJECT POPULATION	15
4.4 EXCLUSION CRITERIA	15
4.5 STUDY OBJECTIVE	16
5. INVESTIGATIONAL PROCEDURES.....	16
5.1 SUBJECT IDENTIFICATION.....	16
5.2 RELEASE OF MEDICAL INFORMATION	17
5.3 DESCRIPTION OF STUDY MEASURES.....	17
5.4 PRE-OPERATIVE PROCEDURE	20
5.5 POST-OPERATIVE PROCEDURE.....	22
6. DATA ANALYSIS.....	27
7. SUMMARY OF DATA COLLECTION VISITS	27
8. REPORTING PROCESS FOR ADVERSE EVENTS AND DEVICE DEFICIENCIES	30
8.1 DEFINITIONS.....	30
8.2 ASSESSMENT AND REPORTING OF ADVERSE EVENTS AND DEVICE DEFICIENCIES	31
8.3 PROTOCOL DEVIATIONS	32
9. STUDY COMPLETION	32
9.1 COMPLETED SUBJECTS	32
9.2 DISCONTINUED SUBJECTS	32
9.3 PREMATURE STUDY TERMINATION	33
10. DATA ANALYSES.....	33
10.1 ADDITIONAL ANALYSES	33
10.2 STUDY POPULATION	34
10.3 MISSING DATA	34
11. RISK BENEFIT STATEMENT.....	34
11.1 BENEFITS	34
11.2 RISKS.....	34
12. GOOD CLINICAL PRACTICES STATEMENT.....	35

12.1	ACCESS TO STUDY DOCUMENTS AND STUDY MONITORING	35
12.2	QUALITY CONTROL AND ASSURANCE	35
12.3	INSTITUTIONAL REVIEW BOARD	35
12.4	INFORMED CONSENT PROCESS.....	35
12.5	CONFIDENTIALITY.....	36
12.6	PROTOCOL DEVIATIONS AND AMENDMENTS.....	36
12.7	DATA MANAGEMENT	37
12.8	RECORD KEEPING AND RETENTION	37
12.9	STUDY REPORT AND PUBLICATION.....	37
13.	REFERENCES.....	37
14.	CHANGE HISTORY.....	38

1. Clinical Investigational Synopsis

Title	An Evidence Based Delivery Model of Care for Adult CI Recipients
Study Sites	Up to 5 sites
Study Duration per subject	Up to 12 months
Study Population	Minimum of 35 and up to 50 Newly implanted postlingually hearing-impaired patients, aged 18 years and older.
Study Overview	
The clinical investigation is evaluating a new clinical model in a group of newly implanted subjects who have already been consented to CI surgery.
 
This randomized multi-center study will investigate a new model (Group A) based on outcome evidence, a standardized programming and testing method that utilizes artificial intelligence and will be compared to a traditional clinical model (Group B).

Primary Objective	To evaluate the total amount of clinical time as defined by number and duration of visits in a new model (Group A) compared to a traditional clinical care schedule (Group B)
Secondary Objectives	
 1. To compare speech perception in quiet as measured on CNC words in the implanted ear. 2. To compare subject hearing outcome satisfaction on the SSQ-12 between the two models. 3. To compare device and accessory use of subjects as measured by a device use questionnaire and datalogging between the two models. 4. To compare clinician satisfaction between the models through a questionnaire. 5. To compare speech perception in noise as measured on AzBio +10 S/N in their everyday listening situation using

	the subjects preferred noise program and accessory if appropriate.
Primary Endpoint	Reduction in the overall number of minutes of cochlear implant appointments over the first 6 months post activation in the new model (Group A) compared to the traditional model (Group B).
Secondary Endpoints	
 1. Speech perception on CNC at 3 and 6 months post activation will be the same or better in the new model group compared to the traditional model. 2. Subjective hearing outcome satisfaction on the SSQ-12 at 6 months post activation will be the same or better in the new model group compared to the traditional model. 3. Device and accessory use will be the same or better at 6 months of device use with the new model compared to the traditional model as measured by a device use questionnaire and datalogging. 4. Clinician satisfaction will be the same or better with the new model when compared to the traditional model at the 6-month interval. 5. Speech perception on Az-Bio +10 S/N at 6 months post activation in the subjects everyday listening condition will be better than the pre-operative score.
Study Inclusion Criteria	
 • Patients who are receiving a commercially approved Nucleus® electrode • 18 years and older • Postlingual onset of hearing loss (onset of hearing loss >two years of age) • Individuals who qualify for cochlear implantation using the clinics current CI candidacy criteria • Individuals who have recently been implanted but not yet had their external device activated

	
 • Willingness to participate in a study and comply with all study requirements • Fluent in spoken English
Study Exclusion Criteria	
 • Ossification or any other cochlear anomaly that might prevent insertion of less than 10 electrodes of the electrode array • Diagnosis of retro-cochlear pathology • Diagnosis of auditory neuropathy • Subject considering an acoustic component in the implanted ear • Unrealistic expectations on the part of the subject regarding the possible benefits, risks, and limitations that are inherent to the surgical procedure and use of the prosthetic device • Unwillingness or inability to comply with all investigational requirements • Severe-profound sensorineural hearing loss >30 years • Previous cochlear implant in the contralateral ear. 
Additional cognitive, medical or social handicaps that would prevent completion of all study requirements as determined by the investigator

Study Intervals	
New Model (Group A): Pre-operative, switch-on, 1-month, 3 month and 6 months
 
Traditional Model (Group B): Pre-operative, switch-on, 1-month, 3 month and 6 months with time measurements for any additional visits included within their typical clinical care schedule.

2. Glossary

Term	Definition
CI	Cochlear Implant
IA	Initial Activation
AE	Adverse Event
IRB	Institutional Review Board
CRF	Case Report Form
SAE	Serious Adverse Event
Direct Connect	Subject evaluation including the Personal Audio Cable or mini-mic outside of the soundfield. Also referred to in separate documents as CoalaLink.
MAP	Individualized listening program created for cochlear implant recipients
AI	Artificial Intelligence: behaves similar to car navigation. Logic based in knowledge, decision making and learning capacity.
Artificial Intelligence (AI) MAP	Map created with AI
AutoMAP	Standardized set of MAPs that are based on averaged proven final maps of CI users at that time the fitting process is finished, and all metrics are met, i.e. tonal audiometry, phoneme discrimination, loudness normality and speech audiometry are on target.
Auditory hierarchy skills	Skills to determine auditory processing ability—or listening success. They develop in a general four-step hierarchy, but all work together and are essential for daily listening. These include detection, discrimination, identification and comprehension.

Psychoacoustic tests	This term is an overarching name for the Speech audiometry, phoneme discrimination, loudness scaling, and audiometry collected via Direct Connect. These tests collect data regarding the auditory hierarchy skills through the cochlear implant. Results from these tests are incorporated into recommendations for the AI MAP.
Pending Outcome Requests (POR)	Additional Psychoacoustic tests recommended by the AI engine to be completed by the audiologist at the next clinical visit.
Usage Data	Custom Sound comes with a wireless data logging capability where key usage information is displayed to track recipients' hearing progress. The collected data will provide insights on user compliance and information to assist in managing programs, sound processor and accessory usage.

3. Introduction

Cochlear implant technology has improved immensely since its inception with significant improvements in hearing abilities, smaller sound processors and opportunities for wireless connectivity. One component of care that has not seen the same amount of change is the aftercare of the cochlear implant (CI) recipient. "Aftercare" includes all clinical care delivered from the switch-on up until the recipient has their annual visit.

Based on data collected through survey's, focus groups and clinical observations, there is no standardized approach to the number of clinical visits, programming methodology or tools and materials used in the aftercare treatment of the Adult CI recipient (Dunn 2018, Global Audiology Focus Group 2018). Patients are typically seen 7-10 times in the first-year post CI surgery regardless of their performance. Changes to the recipient's MAP, usually T and C levels, are typically based only on subjective feedback from the recipient and not based on data. This may be due to several reasons including: inconsistent collection of outcome data due to limited sound booth access, lack of benchmark milestones for performance, uncertainty of what parameters to change based on the data they have obtained or clinician preference. This has resulted in a complex and inefficient delivery model. It is unclear the impact this has on the variability seen in patient outcome and hearing satisfaction. In summary there is no standardization to the traditional model and the model can therefore vary from clinic to clinic.

A standardized evidence based adult delivery model has been created using clinical and recipient milestones, clinical outcomes, an AI based programming tool, standardized test paradigm and defined materials and tools to help guide the professional through the clinical aftercare process.

The clinician milestones were created using global data which includes impedance stabilization within the first 60 days, T and C levels by 3 months and data from the Nucleus® CI532 Cochlear Implant in Adults study which suggests pre-post CNC performance for 80% of the study group was $\geq 20\%$ at 3 months and $\geq 30\%$ at 6 months (M. Bewley, Mining clinical databases: Post-Hoc study 2013; Nucleus CI532 Cochlear Implant in Adults study, Preliminary data 2018) .

A clinical decision support tool using AI and evidence (performance tests) collected through a direct connect system is also used in the model. The recommendations by the AI agent is outcome driven based on data from psychoacoustic tests (Bermejo et al, 2013, Varenberg et al 2011, Govaerts et al 2010). The

psychoacoustic tests represent the auditory hierarchy skills. These include detection, discrimination, identification and comprehension of auditory stimulus. This technique can be utilized as a clinical tool for the audiologist to use in modifying programming parameters for both existing and newly implanted cochlear implant recipients. The AI technology is a tool used by an audiologist to provide programming modifications in a more consistent manner.

The AI system provides several recommendations to potentially improve outcomes, based on data across major cochlear implant systems and individual psychoacoustic data. These Artificial Intelligent recommendations can substantially reduce programming time, by reducing the overall number of programming visits, time taken within the visit, as well as assist the audiologist in implementing changes to the MAP based on evidence to a variety of parameters within the programming software for the average cochlear implant recipient (Battmer et al, 2015).

This system allows for test measures to be presented in a calibrated manner outside of the soundfield through the commercially available wired and wireless programming pods as compared to the traditional sound booth set-up which can be costly. There are several configurations which can be utilized based on clinician and patient preference as well as the sound processor type. One of these configurations is via the commercially available CP910 sound processor, Personal Audio Cable, and standard of care Cochlear Nucleus Programming Pod as shown in Figure 1 below. The software test module may allow for improved clinician and recipient experience by allowing the testing to be delivered directly to the recipient's sound processor outside of a sound booth.

Figure 1. Personal Audio Cable connection

[figure not shown]

Figure 2. AI system interaction

In addition, the evidence-based model provides recipient milestones based on a subjective outcome measure, Client Oriented Scale of Improvement (COSI). This enables the clinician to provide guidance and ways to track their progress during the aftercare process. The final component to the model is the structured use of materials and tools used to support the recipient in successfully using their device and related equipment. The model utilizes self-guided patient materials for device and accessory use.

4. Study Design Overview

The clinical investigation is evaluating a new clinical process in a group of newly implanted subjects.

The new model (Group A) that uses a prescriptive method to deliver CI care in newly implanted adults will be compared to a control method defined as the clinics existing or (Group B) traditional model (i.e. programming, outcome testing completed in a sound booth and materials used for device counseling). The new clinical process standardizes the care model through clinical outcomes, AI based programming, test battery completed through direct connect and tools and materials used for counselling. The goal is to reduce the total amount of clinical time as defined by number and duration of visits compared to the clinics traditional model without compromising clinical outcomes or patient satisfaction.

Group A Study participants will be evaluated during the switch on ,1-month, 3-month and 6-month post op visit. In addition, sound processor and accessory usage data will be collected as well as psychophysical tests completed as part of the clinical decision support tool. Outcome measures will be collected at 3 and 6 months post activation. Total time of the appointment will be collected for each visit using a timer. Programming will be calculated from the CDX file which includes a time stamp. Other activities (accessories, device use, counseling etc.) will be estimated based on subtracting programming time from the total time of the sessions.

- Total time of appointment:
 - Timer will be started when the professional and subject are seated in the consultation room to end the session.
- Programming time
 - Will be extracted from the CDX file based on the time stamps within the session file.

- Other activities (accessories, device use, counseling etc.)
 - Will be estimated based on subtracting programming time from the total time of the sessions.
 - Note: Data entry or forms associated with data collection are not included in the total time of the appointment

Group B subjects will be evaluated at each clinic visit as part of the clinics traditional model on sound processor and accessory usage data. The same three-time measurements will be collected for each visit as Group A. Outcome measures will be collected at 3 and 6 months post activation. Total time of the appointment will be collected for each visit using a timer. Programming will be calculated from the CDX file which includes a time stamp. Other activities (accessories, device use, counseling etc.) will be estimated based on subtracting programming time from the total time of the sessions.

- Total time of appointment:
 - Timer will be started when the professional and subject are seated in the consultation room to end the session.
- Programming time
 - Will be extracted from the CDX file based on the time stamps within the session file.
- Other activities (accessories, device use, counseling etc.)
 - Will be estimated based on subtracting programming time from the total time of the sessions.
 - Note: Data entry or forms associated with data collection are not included in the total time of the appointment

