4.5 Study Objective

4.5.1 Primary Objectives

Primary Objective

To evaluate the total amount of clinical time as defined by number and duration of visits in a new model (Group A) compared to a traditional clinical care schedule (Group B).

Secondary Objectives

1. To compare speech perception in quiet as measured on CNC words in the implanted ear.
2. To compare subject hearing outcome satisfaction on the SSQ-12 between the two models.
3. To compare device and accessory use of subjects as measured by a device use questionnaire and datalogging between the two models.
4. To compare clinician satisfaction between the models through a questionnaire.
5. To compare speech perception in noise as measured on AzBio +10 S/N in their everyday listening situation using the subjects preferred noise program and accessory if appropriate.

5. Investigational Procedures

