In addition, one list of AzBio +10 S/N at S0N0 in the sound field in the two-ear listening condition using the subjects preferred noise program and accessory if appropriate will be completed in a calibrated sound booth.

Two lists of CNC words of 50 monosyllabic words in CD format will be administered in quiet at a level equal to 60dBA in the soundfield and scored as total number of words correct, which will be expressed as a percentage correct for this study. Subjects will be tested in the unilateral condition using a configuration of speech at 0° azimuth in quiet in a calibrated sound booth.

The following speech perception tests will be administered to the traditional model group (Group B):

- One list of AzBio +10 S/N at S0N0 in the sound field in the two-ear listening condition using the subjects preferred noise program.
- Two lists of CNC words of 50 monosyllabic words in CD format will be administered in quiet at a level equal to 60dBA in the soundfield and scored as total number of words correct, which will be expressed as a percentage

correct for this study. Subjects will be tested in the unilateral condition using a configuration of speech at 0° azimuth in quiet in a calibrated sound booth.

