5.4.3 Candidacy Baseline Assessment

The clinic will administer their typical candidacy baseline assessment for patients receiving a cochlear implant as standard of care. In addition, they will administer the following, if not part of the standard battery:

- New Model (Group A) and Traditional Model (Group B)
 - CNC Words: Two lists at 60 dBA with an appropriately fit hearing aid in the unilateral condition (contralateral ear plugged)
 - AzBio Sentences in Noise at 60 dBA at +10 dB S0N0 presented in the sound field for the everyday listening condition.
 - Patient reported outcomes:
 - SSQ-12
 - COSI
 - Hearing History: Information collected from the subject regarding the type and duration of their hearing loss.
 - Demographics: Characteristics of the subject population to include race, ethnicity and gender etc.
 - Device History: Current and previous use of hearing aids
 - Medical History: current or past medical conditions or surgical history relevant to the conduct of the study
- Eligibility: confirmation subject meets inclusion and exclusion criteria
- Randomization: Upon randomization, Group A subjects will receive the following:
 - A take home packet (at the candidacy evaluation or post-surgery) prior to the switch-on to provide them with information they will review as part of the self- learning.
 - Written instructions for scheduling a support call with Cochlear Recipient Services for counselling on external equipment and cochlear implant system. Call will be scheduled 2 weeks following initial activation.

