5.5.5 Six Months Post activation

At 6 months post activation, the following procedures will be completed:

- New Model (Group A)
 - Confirm Device use through usage data screen in Custom Sound
 - Administer psychoacoustic tests to include:
 - Any pending outcomes requests from 3-month visit
 - Speech Audiometry
 - Obtain FOX Advice
 - Review CNC performance at 70dB on speech audiometry to determine if recipient tracking to ≥ 30 pre-post improvement on CNC words
 - If subject meets above criteria and AI has no other recommendations (Green/Teal FOX): Provide AI MAP for take home use.
 - Complete patient reported COSI and SSQ-12
 - Complete Clinician reported Materials/Tools questionnaire
 - Complete Clinician satisfaction questionnaire
 - Complete subject Service Satisfaction Questionnaire
 - Evaluate hearing options for contralateral ear
 - CNC Words: Two lists of 50 monosyllabic words at 60 dBA in the soundfield using a configuration of speech at 0° azimuth in quiet for the implanted ear (contralateral ear plugged)
 - AzBio Sentences in Noise at 60 dBA at +10 dB S0N0 presented in the soundfield for the everyday listening condition
 - Communication Documentation form
 - An anonymized .cdx file will be provided to the study sponsor
 - If the subject does **not** meet above criteria (≥ 30 CNC words) and AI has made modifications to the fitting and wants additional outcome measures, complete as requested.

- Complete patient reported COSI and SSQ-12
- Complete Clinician reported Materials/Tools questionnaire
- Complete clinician satisfaction questionnaire
- Complete subject Service Satisfaction Questionnaire
- Evaluate hearing options for contralateral ear
- CNC Words: Two lists of 50 monosyllabic words at 60 dBA in the soundfield using a configuration of speech at 0° azimuth in quiet for the implanted ear (contralateral ear plugged)
- AzBio Sentences in Noise at 60 dBA at +10 dB S0N0 presented in the soundfield for the everyday listening condition
- An anonymized .cdx file will be provided to the study sponsor.
- If CNC word score at 70 dB on speech audiometry remains less than 30% after completing the above steps, it is recommended the patient be seen in 1 month using standard clinical procedures using Custom Sound directed by CTM Cochlear staff.
- Traditional Model (Group B)
 - Programming and/or counselling as defined by Center
 - Communication documentation form

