 - CNC Words: Two lists of 50 monosyllabic words at 60 dBA in the soundfield using a configuration of speech at 0° azimuth in quiet for the implanted ear
 - AzBio Sentences in Noise at 60 dBA at +10 S0N0 presented in the soundfield for the everyday listening condition with accessory is appropriate
 - Complete COSI, SSQ-12 and subject Service Satisfaction Questionnaire
 - An anonymized. cdx file will be provided to the study sponsor

6. Data Analysis

Statistical Analysis for this study is addressed in detail in the document entitled "Statistical Analysis Plan for the Evidence Based Delivery Model of Care for Newly Implanted Adult CI Recipients".

7. Summary of Data Collection Visits

Each subject will participate in 4-6 scheduled evaluation sessions. For Group A, subjects will be seen preoperatively, at switch-on and at 1, 3, 6 post activation. Visit windows are restricted for the switch on, 1, 3 and 6 month, and deviations from these intervals by more than the windows indicated in the table below.

Unscheduled visits should be documented on the form indicated above in section 5.3.1.4.

Table 1: Data Collection Visit Schedule Group A

Measure	Pre-Op	Switch - on	Video Conference (+/- 1 week)	1 mth (+/- 3 weeks)	3 mth (+/- 3 weeks)	6 mth (+/- 3 weeks)
Informed Consent	X					
Clinician Sat.						X
Hearing History	X					
Medical History	X					
Demographics	X					
Eligibility	X					
Device History	X					
Time measurement		X		X	X	X
Comm. Doc.			X	X	X	X

Form						
CNC Words	X				X	X
Az Bio +10	X					X
Usage Data				X	X	X
Service Satisfaction		X				X
SSQ	X					X
Rehab Screener				X		
COSI	X				X	X
Mat.-Tools Q.		X		X	X	X
AEs and DDs		X		X	X	X

For Group B, subjects will be seen preoperatively, at switch-on, 1-2 weeks, and at 1, 3, 6 post activation. Visit windows are restricted and deviations from these intervals by more than +/- 1 week for the video conference (Group A) and 1-2 week follow-up (Group B), and +/- 3 weeks for all other visits will be reported on in the clinical investigation report.

Unscheduled visits should be documented on the form indicated above.

Table 2: Data Collection Visit Schedule Group B

Measure	Pre-Op	Switch - on	1-2 weeks (+/- 1 week)	1 mth (+/- 3 weeks)	3 mth (+/- 3 weeks)	6 mth (+/- 3 weeks)
Informed Consent	X					
Clinician Sat.						X

Medical History	X					
Device History	X					
Hearing History	X					
Demographics	X					
Eligibility	X					
Time measurement		X	X	X	X	X
Comm. Doc. Form			X	X	X	X
Service Satisfaction		X				X

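### The AzBio endpoint is judged only against the pre-operative score, not between care models, and the rule on using an accessory during the test changes arm between sections

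*Protocol*

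**What the plan says.** **Endpoint and objective.** The Protocol synopsis describes a randomised comparison of a new care model (Group A) with the traditional one (Group B). Secondary endpoints 1 to 4 (CNC words, SSQ-12, device and accessory use, clinician satisfaction) each require the new model to be no worse than the traditional model. Endpoint 5 reads "Speech perception on Az-Bio +10 S/N at 6 months post activation in the subjects everyday listening condition will be better than the pre-operative score". It names no group and no between-model contrast. Objective 5 (synopsis and Section 4.5.1) is to compare speech perception in noise on "AzBio +10 S/N in their everyday listening situation using the subjects preferred noise program and accessory if appropriate". The design goal in Section 4 is to cut clinical time "compared to the clinics traditional model without compromising clinical outcomes or patient satisfaction".

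**Test condition.** The accessory instruction appears in four places:

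- Objective 5 allows an accessory where appropriate and does not distinguish arms.
- Section 5.3.1 has Group A tested "in the two-ear listening condition using the subjects preferred noise program and accessory if appropriate will be completed in a calibrated sound booth". The Group B bullet stops at the noise program: "one list of AzBio +10 S/N at S0N0 in the sound field in the two-ear listening condition using the subjects preferred noise program".
- Section 5.5.5 has Group A at 6 months tested with "AzBio Sentences in Noise at 60 dBA at +10 dB S0N0 presented in the soundfield for the everyday listening condition", with no accessory in either Group A branch. The Group B bullet has the test "presented in the soundfield for the everyday listening condition with accessory is appropriate".
- Section 5.4.3 (baseline, both groups) has "AzBio Sentences in Noise at 60 dBA at +10 dB S0N0 presented in the sound field for the everyday listening condition" and does not mention an accessory.

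Section 5.4.2 also accepts AzBio scores obtained up to 90 days before consent as part of the pre-operative evaluation.

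**The concern.** A gain from before to after implantation is expected in both arms, because both are implanted between the two tests. A test against the pre-operative score therefore makes no use of the randomisation and cannot show whether speech in noise is preserved under the new model. AzBio is the only speech-in-noise test scheduled in both arms (Tables 1 and 2), so no other measure fills this gap. CNC and SSQ-12 already have between-model endpoints, so the gap concerns AzBio only.

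The accessory wording raises a separate problem of measurement. A site that follows Section 5.3.1 literally may allow an accessory in Group A only; one that follows Section 5.5.5 may allow it in Group B only. Either way the test condition depends on arm, and the direction of bias depends on which section was read. Under one common rule, by contrast, a difference in accessory use would be partly an effect of the care model. An accessory used at 6 months but not at baseline could also inflate the pre/post change, so the endpoint is exposed even as written.

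**Working it through.** The protocol states no AzBio gain, SD, significance level or power, so there is no figure to reproduce. The check compares the texts and then illustrates the size on stated assumptions.

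**1. Comparator in each secondary objective and endpoint**

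| | Does the objective name the two models? | Endpoint compares with |
|---|---|---|
| 1 CNC | No | Traditional model |
| 2 SSQ-12 | Yes | Traditional model |
| 3 Device and accessory use | Yes | Traditional model |
| 4 Clinician satisfaction | Yes | Traditional model |
| 5 AzBio +10 | No | Pre-operative score |

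Objective 1 also leaves out the two models, yet its endpoint is between-model. The missing phrase in objective 5 therefore does not by itself imply a pre/post comparison.

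**2. Accessory during the AzBio test**

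| Source | Group A | Group B |
|---|---|---|
| Objective 5 | Allowed | Allowed |
| Section 5.3.1 | Allowed | Not mentioned |
| Section 5.5.5 (6 months) | Not mentioned | Allowed |
| Section 5.4.3 (baseline) | Not mentioned | Not mentioned |

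**3. Probability of meeting endpoint 5 when the new model is worse**

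The total sample of 35 to 50 comes from the synopsis. The assumptions are about equal allocation (17 v 18, or 25 v 25), true gains of 15 points in A and 30 in B, an SD of change of 20, 25 or 30, and a two-sided 5% paired t-test. Power comes from the noncentral t distribution with n − 1 degrees of freedom and noncentrality gain/(SD/√n). The protocol does not say whether the test is pooled or per arm, so both are shown.

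Pooled: the mean gain is (15 + 30)/2 = 22.5. The SD is √(SD² + 7.5²), where 7.5 is half the 15-point difference between arms. This gives 21.4, 26.1 and 30.9.

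Group A alone: for example, at n=25 and SD 25 the noncentrality is 15/(25/5) = 3.0.

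| SD of change | Pooled, n=35 | Pooled, n=50 | A alone, n=25 | A alone, n=17 |
|---|---|---|---|---|
| 20 | >0.999 | >0.999 | 0.949 | 0.827 |
| 25 | 0.9986 | >0.999 | 0.821 | 0.642 |
| 30 | 0.987 | 0.999 | 0.670 | 0.491 |

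With a smaller assumed deficit of 10 points (A gains 20, B gains 30), the same formula for A alone gives 0.89 to 0.998 at n=25 and 0.73 to 0.97 at n=17.

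**4. Precision of a between-arm estimate**

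The 95% half-width is t(0.975) × SD × √(1/n_A + 1/n_B). At SD 25:

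- 17 v 18: 2.035 × 25 × √(1/17 + 1/18) = 17.2 points.
- 25 v 25: 2.011 × 25 × √(2/25) = 14.2 points.

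| SD | Half-width, 17 v 18 | Half-width, 25 v 25 | P(interval excludes 0 at a true 15-point deficit), 17 v 18 | Same, 25 v 25 |
|---|---|---|---|---|
| 20 | 13.8 | 11.4 | 0.58 | 0.74 |
| 25 | 17.2 | 14.2 | 0.41 | 0.55 |
| 30 | 20.6 | 17.1 | 0.30 | 0.41 |

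Adjusting for a baseline score with an assumed correlation of 0.5 multiplies the SD by √(1 − 0.25) = 0.866. At SD 25 the half-widths become 14.9 (17 v 18) and 12.3 (25 v 25).

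**5. Bias if an accessory were allowed in one arm only**

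Bias = share using it × its effect. For an assumed share of 25% to 75% and an effect of 5 to 15 points, the range runs from 0.25 × 5 = 1.25 to 0.75 × 15 = 11.25 points.

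**The case against.** The strongest reply on the endpoint is that objective 5 names no comparator and endpoint 5 supplies one, just as endpoint 1 does for objective 1. On that reading the two do not contradict each other, and a within-subject secondary endpoint is simply weaker evidence. Section 6 leaves the analysis to an SAP that was not available for this review, and Section 10.1 lists an evaluation of site differences in time and outcomes between and within groups. This reply stands in part: a pre/post reading is possible, and the SAP may contain a between-arm AzBio analysis. But even a deliberate pre/post endpoint cannot serve the Section 4 goal, and the Section 10.1 item concerns sites and does not name AzBio.

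On the accessory, nothing forbids one in either arm. Read together with objective 5, the sections can be taken to allow it in both. It is also fair that Section 5.4.3 defines the baseline test in every respect except the accessory. So bias is a risk that depends on how sites read the text; it has not been shown to occur. The risk remains because these are instructions to sites, and no later analysis can change how a test was run.

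The sizes rest on assumed gains, and near-certain success applies only to the pooled reading. A between-arm comparison at this sample size would also miss a 15-point deficit fairly often. Both limits are accepted.

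**Conclusion.** The concern holds on both counts. As worded, endpoint 5 says nothing about new versus traditional care and can be met when the new model is worse. Under the assumed 15-point deficit, success is nearly certain if the arms are pooled and ranges from about even to likely in Group A alone. Separately, the accessory clause sits with opposite arms in Sections 5.3.1 and 5.5.5. Literal use of either section in one arm only could shift the between-arm difference by roughly 1 to 11 points on the assumed inputs.

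The text findings are firm. All the sizes are illustrations, because the protocol gives no AzBio gain, SD, allocation ratio or accessory effect. This is a secondary endpoint and should be fixed; it does not affect the primary comparison of clinical time.

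**What to change.** 1. Restate endpoint 5 as the Group A minus Group B difference in 6-month AzBio +10, adjusted for the pre-operative AzBio +10 score, with a 95% CI. Label it supportive and keep the pre/post change in each arm as descriptive.
2. Reconcile Sections 5.3.1, 5.4.3 and 5.5.5 with objective 5 so that one identical noise-program and accessory rule applies to both arms. Which rule to adopt is for the sponsor and investigators to decide.
3. Add a CRF field recording whether an accessory was used at each AzBio test, including pre-operative scores taken from clinic records.

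The cost is wording in the endpoint and three sections, plus one CRF field. AzBio is already scheduled in both arms pre-operatively and at 6 months. The new estimate will show direction and size, but with the half-widths above it will not by itself prove that speech in noise is preserved, and the report should say so.
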